8.2 Secondary Objectives

KEY SECONDARY OBJECTIVE

- To demonstrate weight loss efficacy by achieving a greater proportion (%) of subjects with at least a 5% reduction in BMI during 52 weeks of treatment with Belviq XR 20 mg administered QD as compared to placebo

OTHER SECONDARY OBJECTIVES

- To demonstrate weight loss efficacy by achieving a greater proportion (%) of subjects with at least a 5% reduction in BMI after an initial 12 weeks of treatment with Belviq XR 20 mg administered QD compared to placebo
- To demonstrate that achieving at least a 5% reduction in BMI after an initial 12 weeks of treatment with Belviq XR 20 mg administered QD is predictive of sustained change in BMI during 52 weeks of treatment with Belviq XR 20 mg administered QD
- To demonstrate weight loss efficacy by percentage change from baseline in BMI during 52 weeks of treatment with Belviq XR 20 mg administered QD compared to placebo (revised per Amendment 01)
- To demonstrate the efficacy of treatment with Belviq XR 20 mg QD by assessing:
 - Other weight loss effects (eg, proportion [%] of subjects achieving at least a 10% BMI reduction, change in waist circumference) at the end of 52 weeks of treatment
 - Effects on fasting plasma glucose, hemoglobin A1c (HbA1c), insulin levels, and Homeostatic Model Assessment of Insulin Resistance (HOMA-IR); glucose [mg/dL] × insulin [mU/L]/405) in subjects with T2DM at baseline during 52 weeks of treatment (revised per Amendments 03 and 04)
 - Effects on fasting plasma glucose, HbA1c, insulin levels, and HOMA-IR; glucose [mg/dL] × insulin [mU/L]/405 in subjects without T2DM at baseline during 52 weeks of treatment (revised per Amendments 03 and 04)
 - Effects on body fat and lean mass composition by Dual-energy X-ray Absorptiometry (DEXA) in a subset of subjects (selected prior to randomization at selected sites) during 52 weeks of treatment (revised per Amendment 03)
 - Changes in cardiovascular risk factors associated with obesity (eg, hypertension, dyslipidemia) including fasting lipid changes (total cholesterol, triglycerides, high density lipoprotein [HDL], low density lipoprotein [LDL]), systolic and diastolic blood pressure, and heart rate) during 52 weeks of treatment (revised per Amendment 03)

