9.7.1.1.2 SECONDARY EFFICACY ENDPOINTS

KEY SECONDARY ENDPOINT

- Proportion (%) of subjects achieving at least a 5% BMI reduction at Week 52

OTHER SECONDARY ENDPOINT

- Proportion (%) of subjects achieving at least a 5% BMI reduction at Week 12
- Proportion (%) of subjects achieving at least a 10% BMI reduction at Week 52
- Percentage change in BMI from baseline to Week 52
- Association between change and percentage change in BMI from baseline to Week 52 with the outcome of achieving at least a 5% BMI reduction at Week 12 (revised per Amendment 02)
- Association between the proportion (%) of subjects achieving at least a 5% or 10% BMI reduction at Week 52 with the outcome of achieving at least a 5% BMI reduction at Week 12 (revised per Amendment 02)
- Change in waist circumference from baseline to Week 52
- Change in total body composition (total fat and lean mass) in a subset of randomized subjects at end of 52 weeks of treatment (revised per Amendment 03)
- Change in HbA_{1c} from baseline to Week 52 for subjects with T2DM at baseline (revised per Amendment 03)
- Change in fasting plasma glucose, fasting insulin, and HOMA-IR from baseline to Week 52 for subjects with T2DM at baseline (revised per Amendments 03 and 04)
- Change in fasting plasma glucose, fasting insulin, and HOMA-IR from baseline to Week 52 for the subjects without T2DM at baseline (revised per Amendments 03 and 04)
- Change in BP (systolic and diastolic) and heart rate from baseline to Week 52
- Change in fasting lipid profile (total cholesterol, LDL cholesterol, HDL cholesterol, triglycerides) from baseline to Week 52
- Proportion (%) of subjects with prehypertension or primary hypertension at Week 52
- Proportion (%) of subjects with dyslipidemia at Week 52
- Subject compliance rate at each visit by pill count during 52 weeks of treatment (per Amendment 03)

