Unless specified, for all other secondary efficacy endpoints, the continuous variables will be analyzed using mixed effect model repeated measurement analysis (MMRM) on the FAS for study treatment compared to placebo, as appropriate. The model will include all data and will include treatment, time, and the interaction of treatment by time as fixed effects, with adjustment for sex (male versus female), BMI and age at baseline, and subject as a random effect. (revised per Amendment 03)

Treatment by time interaction will be used to construct the treatment comparisons at a specific time. The MMRM model assumes that the missing data are missing at random and makes use of all available data even if a subject has missing data at some postbaseline visits. An unstructured covariance matrix will be used, and if the model fails to converge, then an autoregressive matrix will be used. (revised per Amendment 03)

Categorical variables will be analyzed using the Cochran Mantel Haenszel test, Chi-square test, or logistic regression as appropriate. Additional analysis may be performed as needed using appropriate statistical methodologies as specified in SAP.

Subgroup analyses will be performed on the primary efficacy endpoint, including sex (male and female), race (American Indian or Alaska Native, Asian, Black or African American, Native Hawaiian or other Pacific Islander, or White), and age. Additional subgroups may be explored, if deemed necessary. (revised per Amendment 03)

No adjustment for multiplicity is planned for other secondary endpoints, subgroup, and sensitivity analyses.

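### Fasting insulin, HOMA-IR and triglycerides default to absolute change in an MMRM without their own baseline; if they are right-skewed, precision is lost

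*Protocol*

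**What the plan says.** Section 9.7.1.1.2 lists these endpoints as plain change from baseline. Insulin and HOMA-IR appear twice, as "Change in fasting plasma glucose, fasting insulin, and HOMA-IR from baseline to Week 52 for subjects with T2DM at baseline" and "Change in fasting plasma glucose, fasting insulin, and HOMA-IR from baseline to Week 52 for the subjects without T2DM at baseline". Triglycerides appear within "Change in fasting lipid profile (total cholesterol, LDL cholesterol, HDL cholesterol, triglycerides) from baseline to Week 52". The same list names a relative scale where one is wanted, and does so only for BMI: "Percentage change in BMI from baseline to Week 52". Plain change therefore reads most naturally as an arithmetic difference.

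Section 9.7.1.6 gives the analysis. Its default applies unless something else is specified: "the continuous variables will be analyzed using mixed effect model repeated measurement analysis (MMRM) on the FAS for study treatment compared to placebo". A closing qualifier limits this rule to cases where it is appropriate. The model has treatment, time and their interaction, "with adjustment for sex (male versus female), BMI and age at baseline, and subject as a random effect". No log scale, ratio, geometric mean or rank method is named for these endpoints. The section leaves additional analyses to the SAP.

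Section 8.2 defines HOMA-IR as a product: "HOMA-IR; glucose [mg/dL] × insulin [mU/L]/405 in subjects without T2DM at baseline during 52 weeks of treatment". The protocol states no distribution, SD or expected effect for insulin, HOMA-IR or triglycerides.

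**The concern.** A variable built by multiplication changes proportionally, and the absolute size of a proportional change grows with the baseline. If insulin, HOMA-IR and triglycerides have long right tails, the residual variance of their absolute change comes largely from a few subjects with high values, and a treatment effect that is steady in relative terms is measured against that noise.

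The covariate set adds to the problem. Baseline BMI is the outcome's own baseline when the outcome is BMI, but not when it is insulin or triglycerides. For those endpoints the default omits what is usually the most useful covariate.

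What is at stake is the precision of the metabolic objectives, which Section 8.2 states separately for subjects with and without T2DM.

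**Working it through.** **The protocol's own figures.** Section 9.7.2 assumes 130 per arm and 40% dropout, so 130 × 0.6 = 78 per arm. For a BMI difference of 1 kg/m² and SD 2.2, power at 78 per arm is 81.0% (80.5% with the noncentral t), against at least 80% stated. For 20% vs 40% responders it is 78.4%, against more than 78% stated. Both reproduce, but they concern BMI only. From them I take only the 78 per arm.

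**Assumptions not in the protocol.** Lognormal baseline and Week 52 values with the same log-SD *s*; log-scale correlation ρ = 0.6; true active-to-placebo ratio 0.80; one post-baseline timepoint instead of the full MMRM; two-sided 5%. The baseline median is set to 1, which does not affect power.

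**Formulas.**

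Log scale with own log baseline: effect = |ln 0.80| = 0.223; SE = *s*·√(1−ρ²)·√(2/78) = *s* × 0.8 × 0.160.

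Absolute change without own baseline: effect = 0.20·exp(*s*²/2). Variance of change in placebo = 2e^{s²}(e^{s²} − e^{ρs²}). Variance in active = e^{s²}[(0.64 + 1)(e^{s²} − 1) − 1.6(e^{ρs²} − 1)]. SE = √[(sum of the two variances)/78].

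Power ≈ Φ(effect/SE − 1.96).

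| log-SD | Absolute: effect / SE | Power | Log + own baseline: effect / SE | Power |
|---|---|---|---|---|
| 0.4 | 0.217 / 0.064 | 93% | 0.223 / 0.051 | 99% |
| 0.6 | 0.239 / 0.114 | 55% | 0.223 / 0.077 | 83% |
| 0.8 | 0.275 / 0.196 | 29% | 0.223 / 0.102 | 59% |

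**Simulation.** 3,000 trials per setting, all analyses adjusted for a covariate behaving like baseline BMI:

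| log-SD | Absolute, as written | Absolute + own baseline | Log only | Log + own baseline |
|---|---|---|---|---|
| 0.2 | 100% | 100% | 100% | 100% |
| 0.4 | 93% | 98% | 97% | 99% |
| 0.6 | 55% | 70% | 73% | 81% |
| 0.8 | 29% | 42% | 49% | 58% |

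The simulation standard error near 55% is √(0.55 × 0.45/3000) = 0.9 points. Repeating it gave 92%, 57% and 30% for the model as written and 99%, 82% and 58% for log with own baseline, at log-SD 0.4, 0.6 and 0.8.

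**Splitting the gap.** With own baseline in both analyses, the log scale alone gains about 1, 10 and 16 points at log-SD 0.4, 0.6 and 0.8. At 0.6, adding the own baseline to absolute change gains 15 points (55% to 70%), nearly as much as the log scale alone gains over the model as written (18 points, 55% to 73%).

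**Sensitivity at log-SD 0.6, as written vs log with own baseline.** Correlation 0.4: 42% vs 71%. Correlation 0.8: 83% vs 97%. With 104 per arm (80% of 130, the assessment target in Section 9.5.1.3): 69% vs 92%.

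**Weight of extremes.** The four most extreme of 156 subjects supply 25%, 33% and 43% of the within-group sum of squares of absolute change at log-SD 0.4, 0.6 and 0.8, against 17% on the log scale.

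**Validity.** With no treatment effect and 78 per arm, rejection rates are 4.4% to 5.8% across all four analyses. At 12 per arm, a size I chose because the protocol states none for the T2DM subgroup, rates on absolute change were 3.8% to 5.3%.

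**The case against.** The strongest reply is that transformation belongs to the SAP, which is not at hand. The protocol never says the data are untransformed. The MMRM is a default that yields where something else is specified and applies as appropriate, and change in log value is still a change from baseline. A reader might infer that the protocol forbids transformation or locks in the raw scale. The text does not support that, because absolute change is only its natural reading. What remains is that Section 9.7.1.1.2 has named the quantity, Section 9.7.1.6 spells out the model down to its covariance structure, and its explicit deferral to the SAP concerns additional analyses. This is a written default that can be improved, not a missing detail.

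Second, the skewness is assumed. Only the product form of HOMA-IR is documented. Lognormal data with a constant ratio favor the log model by construction, and the loss is small at log-SD 0.4 and nil at 0.2. This stands, and it is why the size is given as a range.

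Third, a reader might infer that the test is unreliable in a small T2DM subgroup. The null simulations do not show that: the error rate stays near or slightly below 5%. Nor was it shown that a conclusion would turn on one or two subjects, only that extremes carry more weight.

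Finally, a geometric mean ratio and a difference in mean change are different estimands. Preferring the ratio is a judgment, though a natural one for a product.

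**Conclusion.** The point holds as a minor improvement in efficiency. As written, the default for these three endpoints is absolute change adjusted for baseline BMI, age and sex, without the endpoint's own baseline. Under the assumptions above, the power lost against the log scale with own log baseline is about 7 points at log-SD 0.4 (99 − 92), 25 at 0.6 (82 − 57) and 28 at 0.8 (58 − 30). A substantial part of that comes from the missing own baseline rather than from the scale. Nothing in the protocol shows where the true log-SD lies, and the single-timepoint calculation only approximates the MMRM. False positives do not increase. These are other secondary endpoints without multiplicity adjustment, so the primary and key secondary conclusions are untouched.

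**What to change.** Add one sentence to Section 9.7.1.6, before unblinding: fasting insulin, HOMA-IR and triglycerides are analyzed in the MMRM as change in log value, with the endpoint's own log baseline added to the covariates, and reported as geometric mean ratios with 95% confidence intervals. Keep arithmetic change as a descriptive summary. This addresses both the scale and the missing baseline, and it removes a later choice between scales.

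The cost is a log transform and one extra covariate. The downside is that the effect reads as a relative rather than an absolute difference, which the descriptive summaries partly offset.

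### The repeated-measures model for the continuous secondary endpoints omits each endpoint's own baseline, which costs precision but not validity

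*Protocol*

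**What the plan says.** The current protocol (v10.0), Section 9.7.1.6, Other Secondary Efficacy Analyses, applies a mixed model for repeated measures to all other continuous secondary endpoints unless something else is specified. The covariate part of the model reads "with adjustment for sex (male versus female), BMI and age at baseline, and subject as a random effect". Apart from that, the text names only "treatment, time, and the interaction of treatment by time as fixed effects". No further covariate is named. The shorter synopsis text names the method without covariates.

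Section 9.7.1.1.2 defines most of the endpoints concerned as changes from baseline, for example:

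- For anthropometry: "Change in waist circumference from baseline to Week 52"
- For vital signs: "Change in BP (systolic and diastolic) and heart rate from baseline to Week 52"
- For the lipid measures: "Change in fasting lipid profile (total cholesterol, LDL cholesterol, HDL cholesterol, triglycerides) from baseline to Week 52"

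HbA1c, fasting glucose, fasting insulin, HOMA-IR and DEXA body composition are treated in the same way. The list also contains "Percentage change in BMI from baseline to Week 52", for which baseline BMI is the own baseline.

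Three other places bear on the point. The primary ANCOVA in Section 9.7.1.6 has baseline BMI as a covariate for change in BMI, so it does adjust for its own baseline. Table 2 (Section 9.5.2.1) schedules all the measurements behind these endpoints at Visit 2, with DEXA at selected sites only. Section 9.4.3 stratifies randomization by sex alone.

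**The concern.** The secondary model carries over the covariates of the primary analysis, where baseline BMI is the outcome's own baseline. For blood pressure or triglycerides it is not, so the model compares change scores without adjusting for what is usually their strongest predictor.

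Two things follow. The residual variance is larger than it need be. Also, because change is negatively related to the starting value, an arm that happens to start higher will tend to fall further whatever its treatment. Stratification by sex does not balance these baselines. At stake is the precision and the reading of the metabolic, cardiovascular and body-composition results, not the primary or key secondary conclusion.

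**Working it through.** **The plan's own figures.** Section 9.7.2 assumes SD 2.2 kg/m², a 1 kg/m² difference, 130 per arm and 40% dropout, which leaves 130 × 0.6 = 78 per arm. Power is 81.0% by the normal approximation and 80.5% by the noncentral t, against at least 80% stated. For 20% versus 40% responders it is 78.4%, against greater than 78% stated. Both reproduce, and neither depends on the model in question. No power is stated for the continuous secondary endpoints.

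**Precision.** Let s be the SD of the endpoint, taken as equal at baseline and Week 52, and r the correlation between the two. The documents give no r; 0.4 to 0.9 is an assumption.

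- Variance of the change score: 2s²(1 − r)
- Residual variance after own-baseline adjustment: s²(1 − r²)
- Ratio, adjusted to unadjusted: (1 + r)/2
- Confidence interval width scales with the square root of that ratio.
- Subjects needed by the stated model for equal precision: 2/(1 + r) times as many.
- Power without the term, where it would be 80% with it: Φ(2.802 × √((1 + r)/2) − 1.960)

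| r | ratio | variance cut | interval narrower by | subjects, stated model | power without the term |
|---|---|---|---|---|---|
| 0.4 | 0.70 | 30% | 16% | 1.43× | 65% |
| 0.5 | 0.75 | 25% | 13% | 1.33× | 68% |
| 0.7 | 0.85 | 15% | 8% | 1.18× | 73% |
| 0.8 | 0.90 | 10% | 5% | 1.11× | 76% |
| 0.9 | 0.95 | 5% | 3% | 1.05× | 78% |

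**Does baseline BMI already do the work?** A version with baseline BMI in both models took its correlation with the endpoint's baseline as 0, 0.3 or 0.5, and with the Week 52 value as 0.9 times that. At r = 0.5 the ratios were 0.750, 0.735 and 0.698, a cut of 25% to 30%. At r = 0.8 they were 0.900, 0.900 and 0.897. At these correlations BMI does not stand in for the own baseline. Stronger correlations, which are plausible for waist and fat mass, were not examined.

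**Chance imbalance.** The standard error of a baseline difference between arms is s√(2/m): 0.124s at m = 130 and 0.160s at m = 78, with 95% ranges of ±0.24s and ±0.31s. A baseline difference d shifts the change-score contrast by (1 − r)d. For r = 0.5 and d = 0.25s the shift is 0.125s. Conditional on that difference, the two-sided false-positive rate is 13.6% at 130 per arm and 8.7% at 78 per arm. At 130 per arm a difference of 0.25s is 0.25/0.124 = 2.0 standard errors, just outside the 95% range, so this is an unfavorable case and not a typical one.

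**The case against.** The strongest objection is that nothing here is invalid. A reader might infer that these comparisons are biased or that their false-positive rate is inflated. The documents do not support that. Under randomization the change-score contrast is unbiased on average, and its ordinary standard error already contains the variation due to chance baseline differences. The conditional rates above describe particular realized imbalances and average out to the nominal level. This stands and limits the point to efficiency and conditional sensitivity.

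Second, the size is assumed. No correlation is given, equal SDs are assumed, and at r = 0.9 the gain is only 5% in variance. This also stands, which is why the range is shown to 0.9 and in interval width as well as variance.

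Third, the wording leaves room: the model is a default, and the SAP may specify otherwise. That tempers the point but does not supply the missing term. The protocol chose to list covariates and left this one out. Nor does the instruction to include all data help. If baseline were placed in the response vector, the stated unconstrained treatment and treatment-by-time terms would leave the Week 52-minus-baseline contrast essentially the unadjusted change difference. Only a constraint of equal baseline means would alter that, and none is stated.

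Fourth, adding terms is not free. Glycemic measures have three scheduled post-baseline visits (Weeks 12, 28 and 52), so an own baseline with its time interaction adds about three parameters to a model with unstructured covariance, in a T2DM subset that has no minimum size. DEXA has one post-baseline scan and a minimum of 30 subjects (Section 9.5.1.5.10), so a time interaction means nothing there. Both observations stand and shape the fix.

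A reader might also infer that the small subsets suffer most. Chance imbalance is larger there in absolute units. But the variance ratio (1 + r)/2 does not depend on sample size, so at a given r the relative loss is the same.

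Last, a reader might extend the point to the prehypertension or hypertension and dyslipidemia proportions. No defect is shown there: Section 9.7.1.6 already permits logistic regression as one option for categorical variables.

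**Conclusion.** The point holds as a loss of precision and a conditional sensitivity to baseline imbalance. It applies to waist, HbA1c, fasting glucose, insulin, HOMA-IR, blood pressure, heart rate, lipids, and fat and lean mass. It does not apply to percentage change in BMI, whose own baseline is in the model, or to pill-count compliance, which has no baseline.

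The size rests on the two assumptions stated above, equal SDs and the range of r. The formulas also compare two time points and do not model the full repeated-measures structure. The affected endpoints lie outside the gatekeeping, carry no multiplicity adjustment and have no stated power, so this is an improvement to supportive analyses. It is worth making because the baselines are already collected and the primary analysis follows the same principle.

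**What to change.** In Section 9.7.1.6, and in the SAP:

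- Add the baseline value of the endpoint to the covariates already listed for the repeated-measures model, with its interaction with time where there is more than one scheduled post-baseline visit. Keep sex, baseline age and baseline BMI. For percentage change in BMI, baseline BMI is that value and enters once.
- Analyze DEXA fat and lean mass by ANCOVA of the Week 52 change, with the own baseline as a covariate and no time terms.
- State in advance that the baseline-by-time interaction may be dropped in the T2DM subset, keeping the own-baseline main effect, and under what condition.

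Leave the analyses of the categorical endpoints as they are. The cost is a short change of wording and a few degrees of freedom: about three parameters for the glycemic measures and one for each DEXA measure. No new data are needed.

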9.7.1.1 Study Endpoints

9.7.1.1.1 PRIMARY EFFICACY ENDPOINT

- Change in BMI from baseline to Week 52

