9.7.1.6 Efficacy Analyses

The FAS will be used as the primary analysis set for all efficacy analyses, while the PP will be used as a supportive analysis. Unless specified otherwise, a 2-sided $\alpha=0.05$ significance level will be used for all efficacy analyses.

Primary Efficacy Analysis

The primary efficacy endpoint is the change in BMI from baseline to Week 52. The change from baseline in BMI will be analyzed using analysis of covariance model (ANCOVA) with factors of treatment, sex (male and female) as fixed effect, and the baseline age and BMI as covariates. The missing values will be imputed using a pattern mixture model utilizing multiple imputation (MI) assuming the missing values are missing not at random (MNAR). The missing values will be imputed at each visit using all available values including the retrieved measurement from the postdiscontinuation data. The details of the analysis model and missing value imputation method will be further described in the SAP.

In addition, the following analyses will also be considered as sensitivity analyses:

- PP analysis: The same primary efficacy analyses described above will be repeated based on the PP.
- Change from baseline in standardized BMI score (Z-score): The same primary efficacy analyses described above will be repeated using Z-score.

Subgroup analyses and additional sensitivity analyses, if appropriate, may also be performed and will be described in the SAP.

Key Secondary Efficacy Analysis

The key secondary efficacy endpoint is the proportion of subjects achieving at least a 5% BMI reduction at Week 52. The secondary efficacy endpoint will be analyzed only if the test for the primary efficacy endpoint is statistically significant.

The proportion of subjects achieving at least a 5% BMI reduction at Week 52 will be analyzed using a logistic regression model with factors of treatment, and sex (male and female), and baseline BMI as a covariate using FAS. Subjects with any missing assessment at Week 52 will be considered as treatment failures in this analysis.

Other Secondary Efficacy Analyses

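### Missing Week 52 BMI is treated as MNAR for absolute change but, by default, as MAR for percentage change, with no reason given

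*Protocol*

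**What the plan says.** Protocol section 9.7.1.1.1 sets the primary endpoint as "Change in BMI from baseline to Week 52". Section 9.7.1.1.2 lists "Percentage change in BMI from baseline to Week 52" among the other secondary endpoints. Section 9.7.1.6 then gives the two endpoints different treatment.

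- **Primary endpoint.** ANCOVA with treatment and sex as factors and baseline age and BMI as covariates, after pattern-mixture multiple imputation, "assuming the missing values are missing not at random (MNAR"). On the data used: "The missing values will be imputed at each visit using all available values including the retrieved measurement from the postdiscontinuation data". The form of the pattern mixture is left open: "The details of the analysis model and missing value imputation method will be further described in the SAP". The same analysis is to be repeated for the BMI Z-score.
- **Key secondary endpoint (5% BMI reduction at Week 52).** Logistic regression, with a missing Week 52 assessment counted as failure.
- **Other continuous secondary endpoints.** "Unless specified, for all other secondary efficacy endpoints, the continuous variables will be analyzed using mixed effect model repeated measurement analysis (MMRM"), fitted on the FAS. Of this model the protocol says "The model will include all data" and "The MMRM model assumes that the missing data are missing at random". No other method is named for percentage change in BMI.

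Sections 9.1 and 9.5.5 keep subjects who stop study drug in follow-up. Section 9.5.1.3 aims for at least 80% of randomised subjects to have the primary assessment, on or off drug. Section 9.7.2 plans the sample size with 40% dropout.

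**The concern.** Percentage change is 100 × (Week 52 BMI − baseline BMI) / baseline BMI. Once baseline is known, it carries exactly the same information as absolute change, and baseline BMI is a covariate in both models. The same subjects lack both outcomes, for the same reasons. If Week 52 BMI is missing not at random given what was observed, so is percentage change. The plan takes one position for the first and the opposite for the second, and does not say why. The BMI Z-score, another rescaling of BMI, does keep the primary method, so percentage change is the odd one out.

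What is at stake is how the two results read together. Section 8.2 names percentage change in BMI as a way to demonstrate weight-loss efficacy, and the adult mean criterion cited in section 7.1.2 is also expressed as a percentage, so readers will look at this estimate. If it differs from the primary result, they cannot tell whether scale or missing-data model is the cause.

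**Working it through.** **1. The plan's own figure.** Inputs from section 9.7.2: difference 1 kg/m², SD 2.2 kg/m², 130 per arm, 40% dropout, two-sided α = 0.05.

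- Evaluable per arm: 130 × (1 − 0.40) = 78.
- Standardised difference: 1 / (2.2 × √(2/78)) = 2.84.
- Power: 81.0% by the normal approximation and 80.5% by the noncentral t.

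The stated power of at least 80% reproduces. I use the 1 kg/m² as the full drug effect below. The ratios do not depend on it, so they apply equally to a mean percentage change.

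**2. Missing subjects lose some or all of the drug effect.** This is an assumption; the protocol does not state it. Let m be the share missing and r the share of the effect that missing subjects keep. With a full effect of 1.00 and nothing recovered from earlier visits, MAR gives 1.00 and the all-randomised effect is 1 − m + m·r. With r = 0 the overstatement is 1/(1 − m) − 1.

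| Missing m | Effect kept r | All-randomised effect | MAR estimate | Overstatement |
|---|---|---|---|---|
| 20% | 0 | 0.80 | 1.00 | 25% |
| 40% | 0 | 0.60 | 1.00 | 67% |
| 20% | 0.5 | 0.90 | 1.00 | 11% |
| 40% | 0.5 | 0.80 | 1.00 | 25% |
| any | 1 | 1.00 | 1.00 | 0% |

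**3. Retrieved off-drug values in the MAR model.** The MMRM uses all data, so BMI measured after stopping drug also enters it. A small simulation checked whether this closes the gap. In it, 40% stop drug in each arm and lose the effect, the true treatment-policy effect is 0.60, and the MAR-type estimate is a within-arm regression on one earlier visit.

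| Share of stoppers retrieved | Still missing | MAR estimate | 0.60 / (1 − m) |
|---|---|---|---|
| 0% | 40% | 1.00 | 1.00 |
| 25% | 30% | 0.85 | 0.86 |
| 50% | 20% | 0.75 | 0.75 |
| 75% | 10% | 0.67 | 0.67 |

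Retrieval shrinks the gap by reducing m but does not remove it. At 20% missing, 0.75 / 0.60 is again 25% too high. In this simulation stopping was unrelated to the earlier visit, so that visit could recover nothing. A full MMRM may recover part.

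**4. A different MNAR form.** Suppose instead that missing subjects in both arms are made worse by 1 kg/m². The MNAR benefit is 1.00 − (share missing on drug) + (share missing on placebo).

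- 40% and 40%: 1.00 − 0.40 + 0.40 = 1.00, so no gap from MAR.
- 30% drug, 50% placebo: 1.00 − 0.30 + 0.50 = 1.20, so MAR (1.00) is the less favourable result.
- 50% drug, 30% placebo: 1.00 − 0.50 + 0.30 = 0.80, so MAR is the more favourable result.

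**The case against.** The strongest reply is that the direction of any gap is unknown. A reader might infer that the MAR analysis is bound to favour the drug. The protocol does not support that: it leaves the pattern-mixture form to the SAP, and step 4 shows forms under which the gap is nil or reversed. This part of the reply stands.

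A reader might also take 67% as the expected size. That needs 40% of Week 52 BMI to be missing, whereas the 40% in section 9.7.2 is a dropout rate for planning, subjects who stop drug stay in follow-up, and the retention target implies no more than 20% missing. It also needs total loss of effect and no help from earlier visits. So 67% is a worst case, and 25% is itself an upper bound at the target.

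Third, the SAP may add a bridging sensitivity analysis, since the protocol allows for further ones. Its absence therefore cannot be claimed. This does not answer the main point: the MMRM under MAR is a method the protocol states for this endpoint, not a detail it defers.

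Finally, percentage change lies outside the gated primary and key secondary tests and has no multiplicity control. That is correct and limits the consequence.

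**Conclusion.** The inconsistency is real. One set of missing BMI values is taken as MNAR for absolute change and, by default, as MAR for percentage change, without a stated reason, so the two results may differ because of the missing-data model alone.

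Its size depends on assumptions the protocol does not fix. If missing subjects have lost the whole drug effect and earlier visits recover nothing, the MAR estimate is too favourable by at most 25% at 20% missing and 67% at 40% missing. If they keep half the effect, the figures are 11% and 25%; if they keep all of it, zero. An equal shift in both arms gives no gap when missingness is balanced, and a reversed one when placebo has more missing data.

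It would be wrong to infer that the trial's main conclusions are in doubt. The primary analysis uses MNAR imputation and the key secondary counts missing as failure; neither relies on the MMRM. The point concerns the consistency of a secondary estimate and is worth correcting because correction is cheap.

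**What to change.** In section 9.7.1.6, name percentage change in BMI as an exception to the MMRM default. In each imputed dataset already created for the primary analysis, compute percentage change from the Week 52 BMI (observed or imputed) and baseline BMI. Fit the same ANCOVA as for the primary endpoint and combine the results by Rubin's rules. Keep the MAR MMRM as a supportive analysis.

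Leave the 10% responder endpoint out of this change. It is categorical and is not assigned to the MMRM. Imputing it would also set it against the missing-as-failure rule for the 5% responder at the same visit.

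The cost is a sentence in the protocol or SAP and one derived variable on datasets that will exist anyway. The downside for the sponsor is a percentage-change estimate that may be less favourable than the MMRM would give.
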